4.2 Discussion of Study Design

Appropriateness of Measurements

Standard statistical, clinical, and laboratory procedures will be utilized in this study. All efficacy measurements in this study are standard parameters used for assessing disease activity in subjects with HCV. All clinical and laboratory procedures in this study are standard and generally accepted.

Suitability of Subject Population

This subject population will include treatment-naïve subjects only. While data from registrational and Phase 2 supportive trials shows that high SVR₁₂ rates can be achieved with 8 weeks of GLE/PIB, slightly lower rates were achieved in treatment-experienced subjects across all GTs. To reduce the risk of Post-Treatment relapse, treatment-experienced subjects will be excluded from this study.

Aminotransferase/platelet ratio index ≤ 1 has been shown to have high sensibility and therefore high predictive negative value in ruling out cirrhosis. It is very likely that the population that will be included in this study using this biomarker will be non-cirrhotic. However, in order to decrease the risk of

enrolling truly cirrhotic subjects, subjects with clinical signs of cirrhosis, history of decompensation, or with lab abnormalities compatible with cirrhosis (low platelets and/or low albumin) will be excluded from this study.

Hepatitis C virus-infected subjects with chronic HCV infection have moderate stable elevations of AST and ALT levels and are considered representative of the population who will receive anti-HCV therapy. This study will include stable subjects with HIV/HCV co-infection, as this sub-population is shown to have similar results as mono-infected treatment-naïve non-cirrhotic subjects with 8 weeks treatment duration in Study M14-730. As HBV co-infected subjects may have some alteration in APRI scores (due to inflammation) and it is difficult to interpret the APRI score in HBV/HCV co-infected population, subjects co-infected with HBV will be excluded from the population.

The age range selected for this study, 18 years of age or older, is also intended to be representative of the target population. Similarly, a substantial portion of the HCV-infected population have a relatively high body mass index, and given the acceptable safety and pharmacokinetic profiles of GLE/PIB in previous studies, this protocol will enroll subjects without a body mass index restriction.

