5 STUDY ACTIVITIES

5.1 Eligibility Criteria

Subjects must meet all of the following criteria in order to be included in the study. Anything other than a positive response to the statements below will result in exclusion from study participation.

Consent

- ✓ 1. Subjects must voluntarily sign and date an informed consent, approved by an Independent Ethics Committee (IEC)/Institutional Review Board (IRB), prior to the initiation of any screening or study-specific procedures.

Demographic and Laboratory Assessments

- ✓ 2. Adult male or female, at least 18 years old at the time of screening.
- ✓ 3. Laboratory values meeting the following criteria within the Screening period prior to the first dose of study drug:
 - Platelets $\geq 150,000$ cells/mm³
 - ALT $\leq 10 \times$ ULN
 - AST $\leq 10 \times$ ULN
 - Direct bilirubin \leq ULN
 - Albumin \geq LLN
 - Calculated creatinine clearance (using Cockcroft-Gault method) ≥ 30 mL/min
 - A negative HBsAg, and negative anti-HBc or; HBV DNA $<$ LLOQ in subjects with isolated positive anti-HBc (i.e., negative HBsAg and Anti HBs)

Disease Activity

- ✓ 4. Positive anti-HCV Ab AND Plasma HCV RNA viral load ≥ 1000 IU/mL at Screening and for at least 6 months before Screening.
- ✓ 5. Any HCV GT allowed, including HCV GT1-, 2-, 3-, 4-, 5-, and/or 6-infection. Mixed GT and indeterminate GT may be acceptable.
- ✓ 6. APRI SCORE ≤ 1 , at time of Screening.

Medical History

- ✓ 7. No history of HCC.
- ✓ 8. No evidence of cirrhosis described as:
 - previous histologic diagnosis of cirrhosis on liver biopsy, e.g., METAVIR, Batts-Ludwig, Knodell, IASL, Scheuer, or Laennec fibrosis score of > 3 , Ishak score of > 4 in any liver biopsy conducted prior to Screening, OR
 - Any previous transient elastography score of ≥ 12.5 kPa, OR
 - Any current or historical clinical evidence of cirrhosis or decompensated cirrhosis, including any current or past evidence of Child-Pugh B or C classification, hepatic encephalopathy or variceal bleeding; radiographic evidence of ascites; or use of lactulose and/or rifaximin for hepatic encephalopathy prophylaxis or treatment.
- ✓ 9. Subject is treatment-naïve, e.g., has never received any other investigational or commercially available anti-HCV agents (e.g., interferon, peginterferon, RBV, telaprevir, boceprevir, simeprevir, asunaprevir, paritaprevir, grazoprevir, daclatasvir, ledipasvir, ombitasvir, elbasvir, dasabuvir, voxilaprevir or any other anti-HCV agent that is approved during the study).

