APPENDIX D. ACTIVITY SCHEDULE

Treatment Period Activity Schedule

The following table shows the distribution of required activities across the screening and 8 week treatment period study visits. The individual activities are described in detail in the **Operations Manual**.

Activity	Screening	DAY 1	WEEK 4	WEEK 8 EOT or Premature Discontinuation
	Day -35 to Day -1	Day 1	Day 28	Day 56 or Day of Discontinuation
INTERVIEWS & PATIENT REPORTED OUTCOMES				
Informed consent	✓			
Evaluation of eligibility criteria	✓	✓		
Medical history	✓	✓		
Adverse event assessment	✓	✓	✓	✓
Prior and concomitant medications assessment	✓	✓	✓	✓
Dispense (d)/Review (r) Study Drug Dosing Card		✓ (d)	✓ (d), (r)	✓ (r)
Patient Reported Outcomes (PROs) Instrument		✓	✓	✓
LABS & EXAMS				
Fibrotest (blinded to site and subject)	✓			
HCV genotype and subtype	✓			
APRI	✓			
12-lead ECG	✓			
Height	✓			
Weight	✓	✓	✓	✓
Vital signs (determinations of systolic and diastolic blood pressure, pulse rate, and body temperature)	✓	✓	✓	✓
Physical examination	✓	✓		✓
Drug/alcohol screen	✓			
FSH (all females)	✓			
Serum pregnancy test (women of childbearing potential only)	✓			
Urine pregnancy test (women of childbearing potential only)		✓	✓	✓
Hematology/chemistry/urinalysis/coagulation panel	✓	✓	✓	✓
Anti-HCV Ab, Anti-HIV Ab	✓			
Hepatitis B panel	✓			
Biomarker pharmacogenetic sample (optional)		✓		

Activity	Screening	DAY 1	WEEK 4	WEEK 8 EOT or Premature Discontinuation
	Day -35 to Day -1	Day 1	Day 28	Day 56 or Day of Discontinuation
HCV RNA samples	✓	✓	✓	✓
HCV resistance sample		✓	✓	✓
HIV-1 RNA (HCV/HIV-1 co-infected subjects only)	✓			
Flow cytometry sample (HCV /HIV-1 co-infected subjects only)	✓			
Biomarker plasma sample	✓	✓	✓	✓
Pharmacokinetic sample			✓	✓
Rx TREATMENT				
Dispense study drug		✓	✓	
Study drug accountability and review of study drug adherence			✓	✓

Post-Treatment Period Follow-Up Activity Schedule

The following table shows the distribution of required activities across the 12 week post-treatment period subject encounters. The individual activities are described in detail in the Operations Manual.

Activity	Post-Treatment WEEK 4	Post-Treatment WEEK 12 or Premature Discontinuation
	Day 84	Day 140 or Day of Discontinuation
INTERVIEWS & PATIENT REPORTED OUTCOMES		
Adverse event assessment	✓	✓
Concomitant medications (all)	✓	
Concomitant medications (for SAEs and HCV)	✓	✓
PRO Instrument		✓
LABS & EXAMS		
Weight	✓	✓

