7.3 Analysis of Laboratory Data

Data collected from the central and local laboratories, including additional laboratory testing due to an SAE, will be used in all analyses. The protocol-defined hematology, clinical chemistry, and urinalysis laboratory tests will be summarized. Some of the above laboratory variables are calculated by the laboratory vendor including indirect bilirubin, creatinine clearance, and eGFR by MDRD.

The baseline value for clinical laboratory tests will be the last non-missing measurement on or before the day of the first dose of study drug. Values on Day 1 must also be before the time of first dose if time is available. The same baseline value will be used for change to Treatment Period visits and change to Post-Treatment Period visits.

Mean changes from baseline to each post-baseline visit, including applicable post treatment visits, will be summarized. Each protocol-specified laboratory parameter will be summarized with the sample size, baseline mean, visit mean, change from baseline mean, standard deviation, minimum, median, and maximum.

The laboratory parameters defined in [Table 1](#) will be assigned a toxicity grade of 1, 2, 3, or 4. The number and percentage of subjects with a maximum toxicity grade of 1, 2, 3 or 4 will be summarized.

Table 1. Definitions of Toxicity Grades 1, 2, 3, and 4 for Laboratory Values

Test	Grade 1	Grade 2	Grade 3	Grade 4
ALT	> ULN – 3 × ULN	> 3 – 5 × ULN	> 5 – 20 × ULN	> 20 × ULN
AST	> ULN – 3 × ULN	> 3 – 5 × ULN	> 5 – 20 × ULN	> 20 × ULN
Alkaline Phosphatase	> ULN – 2.5 × ULN	> 2.5 – 5 × ULN	> 5 – 20 × ULN	> 20 × ULN
GGT	> ULN – 2.5 × ULN	> 2.5 – 5 × ULN	> 5 – 20 × ULN	> 20 × ULN
Total Bilirubin	> ULN – 1.5 × ULN	> 1.5 – 3 × ULN	> 3 – 10 × ULN	> 10 × ULN
Hemoglobin	< LLN – 100 g/L	< 100 – 80 g/L	< 80 g/L	--
White blood cells	< LLN – 3.0 × 10 ⁹ /L	< 3.0 – 2.0 × 10 ⁹ /L	< 2.0 – 1.0 × 10 ⁹ /L	< 1.0 × 10 ⁹ /L
Absolute Neutrophil Count	< LLN – 1.5 × 10 ⁹ /L	< 1.5 – 1.0 × 10 ⁹ /L	< 1.0 – 0.5 × 10 ⁹ /L	< 0.5 × 10 ⁹ /L
Platelet count	< LLN – 75.0 × 10 ⁹ /L	< 75.0 – 50.0 × 10 ⁹ /L	< 50.0 – 25.0 × 10 ⁹ /L	< 25.0 × 10 ⁹ /L
INR	> 1 – 1.5 × ULN	> 1.5 – 2.5 × ULN	> 2.5 × ULN	--
Glucose (increased)	> ULN – 8.9 mmol/L	> 8.9 – 13.9 mmol/L	> 13.9 – 27.8 mmol/L	> 27.8 mmol/L
Glucose (decreased)	< LLN – 3.0 mmol/L	< 3.0 – 2.2 mmol/L	< 2.2 – 1.7 mmol/L	< 1.7 mmol/L
Creatinine	> ULN – 1.5 × ULN	> 1.5 – 3 × ULN	> 3 – 6 × ULN	> 6 × ULN

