Creatinine clearance	< LLN – 60 mL/min	< 60 – 30 mL/min	< 30 – 15 mL/min	< 15 mL/min
Albumin	< LLN – 30 g/L	< 30 – 20 g/L	< 20 g/L	--

Assessment of Hepatotoxicity

The number and percentage of subjects with maximum on treatment lab values meeting the following criteria for potential hepatotoxicity will be summarized:

- ALT $\geq 3 \times$ ULN and total bilirubin $\geq 2 \times$ ULN;
- ALT $\geq 3 \times$ ULN and total bilirubin $< 2 \times$ ULN;
- ALT $> 5 \times$ ULN and total bilirubin $< 2 \times$ ULN;
- ALT $< 3 \times$ ULN and total bilirubin $\geq 2 \times$ ULN.

The number and percentage of subjects with post-baseline values during the Treatment Period meeting the following criteria for hepatic laboratory parameters will be summarized:

- ALT > 5 × ULN and ≥ 2 × baseline;
- AST > 5 × ULN and ≥ 2 × baseline;
- Total bilirubin ≥ 2.0 × ULN and > baseline.

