7.4 Analysis of Vital Signs and Weight

Vital sign variables are body temperature, sitting systolic blood pressure, sitting diastolic blood pressure, sitting pulse rate, and body weight.

The criteria for potentially clinically significant vital sign findings are presented in [Table 2](#).

Table 2. Criteria for Potentially Clinically Significant Vital Sign Values

Test/Measurement	Very Low (VL)	Very High (VH)
Systolic Blood Pressure	≤ 90 mmHg AND A decrease of ≥ 20 mmHg from baseline	≥ 180 mmHg AND An increase of ≥ 20 mmHg from baseline
Diastolic Blood Pressure	≤ 50 mmHg AND A decrease of ≥ 15 mmHg from baseline	≥ 105 mmHg AND An increase of ≥ 15 mmHg from baseline
Pulse Rate	≤ 50 bpm AND A decrease of ≥ 15 bpm from baseline	≥ 120 bpm AND An increase of ≥ 15 bpm from baseline
Weight	A decrease of ≥ 15% from baseline	An increase of ≥ 15% from baseline
Body Temperature		> 38.3°C AND An increase of ≥ 1.1°C from baseline

The baseline value for vital signs will be the last measurement on or before the day of the first dose of study drug. The same baseline value will be used for change to Treatment Period visits and change to Post-Treatment Period visits.

Mean changes from baseline to each post-baseline visit, including applicable post treatment visits, will be summarized. Each vital sign parameter will be summarized with the baseline mean, visit mean, change from baseline mean, standard deviation, minimum, median, and maximum.

The number and percentage of subjects with on-treatment values meeting the specified criteria for Potentially Clinically Significant (PCS) vital sign values (Table 2) will be summarized. A post-baseline value must be more extreme than the baseline value to be considered a PCS finding. A separate listing will be provided that presents all vital sign values for the subjects meeting PCS criteria during treatment.

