For efficacy analyses of HCV RNA and resistance, the time windows specified in [Table 3](#) and [Table 4](#) describe how efficacy data are assigned to protocol-specified time points during the Treatment and Post-Treatment Periods, respectively. All time points and corresponding time windows are defined based on the date/time of blood sample collection.

For laboratory data and vital signs, the time windows specified in [Table 3](#) and [Table 5](#) describes how data are assigned to protocol specified time points.

If more than one assessment is included in a time window, the assessment closest (except in analyses of SVR) to the nominal time will be used. If there are two observations equally distant to the nominal time, the latest one will be used in analyses. For analyses of SVR (e.g., SVR₁₂), the last value in the window will be used.

If multiple measurements are made on the same day for a safety laboratory parameter or a vital sign parameter, the average of the values will be used to calculate descriptive statistics and in analyses of the mean change from baseline. For summaries of shifts from baseline and potentially clinically significant values, multiple values on the same day will not be averaged; all values will be considered for these analyses.

Table 3. Analysis Time Windows for HCV RNA, Resistance Endpoints, Laboratory, Vital Sign Measurements, and PRO Instruments (Treatment Period)

Scheduled Visit	Nominal Day (Study Day)	Time Window (Study Day Range)
Day 1/Baseline ^a	1	≤ 1 ^a
Week 4	28	2 to 42
Week 8	56	43 to 70
Final Treatment Visit ^b	2 to ≤ 2 days after last dose of study drug	

a. Day of first dose of study drug.

b. The last value within the window will be used to define the Final Treatment Visit value. The upper bound of this Final window is Study Drug End Day ≤ 2.

Note: Data must also have Study Drug End Day ≤ 2 for all windows. The result closest to the scheduled time point will be used.

Table 4. Analysis Time Windows for HCV RNA and Resistance Endpoints (Post-Treatment Period)

Scheduled Visit ^a	Nominal Day (Study Drug End Day)	Time Window (Study Drug End Day Range)
Post-Treatment Week 4	28	3 to 56
Post-Treatment Week 12	84	57 to 126
SVR ₄ ^b	28	3 to 56
SVR ₁₂ ^b	84	57 to 126

a. Post-Treatment Visits are applicable to subjects who received at least one dose of study drug.

b. For SVR windows, the last value in the window will be used.

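### SAP 7.3 counts subjects by maximum laboratory grade without reference to baseline, so for 12 of 15 graded rows abnormality already present at entry is counted together with new toxicity

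*SAP*

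**What the plan says.** SAP 7.3, Table 1, assigns Grades 1 to 4 to 15 laboratory rows. Every cut-off is a fixed value or a multiple of the upper or lower normal limit; none refers to the subject's baseline. The summary rule is one sentence: "The number and percentage of subjects with a maximum toxicity grade of 1, 2, 3 or 4 will be summarized". It gives no period for the maximum and no condition on baseline.

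Nearby text is more specific:

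- The hepatic criteria at the end of SAP 7.3 count "subjects with post-baseline values during the Treatment Period meeting the following criteria for hepatic laboratory parameters". They require ALT or AST above 5 × ULN and at least twice baseline, or total bilirubin at or above 2 × ULN and above baseline.
- For vital signs, SAP 7.4 says: "A post-baseline value must be more extreme than the baseline value to be considered a PCS finding".
- SAP 8.0 has a same-day rule that begins "For summaries of shifts from baseline and potentially clinically significant values". Neither 7.3 nor 7.4 lists a shift summary.

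The protocol admits subjects with graded values. In Protocol 5.1 the item beginning "Calculated creatinine clearance (using Cockcroft-Gault method" sets a floor of 30 mL/min, and ALT and AST may be up to 10 × ULN. Protocol 4.2 describes the population as having "moderate stable elevations of AST and ALT levels".

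**The concern.** Safety is part of the primary objective (Protocol 3.1, SAP 4.1) and the trial has one arm. No control group shows how much laboratory abnormality would be seen without the drug, so each subject's baseline is the only internal reference. A maximum-grade table that ignores baseline mixes two kinds of subject: those who arrived with an abnormal value and kept it, and those whose value became abnormal or worsened on treatment. A reader of the table cannot separate them. What is at stake is the interpretation of the laboratory safety table, not the efficacy conclusion.

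**Working it through.** There is no stated figure to reproduce. The check is a count of rows, a grading of the entry limits, and a walk-through of the counting rule.

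**1. Rows with and without a count that refers to baseline**

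The rows of SAP Table 1 are ALT, AST, alkaline phosphatase, GGT, total bilirubin, hemoglobin, white cells, neutrophils, platelets, INR, glucose increased, glucose decreased, creatinine, creatinine clearance and albumin: 15 rows.

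The hepatic criteria in SAP 7.3 cover ALT, AST and total bilirubin: 3 rows.

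15 − 3 = 12 rows without such a count.

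The three covered rows have one threshold each. For ALT and AST it lies at the start of Grade 3 (above 5 × ULN). For total bilirubin it lies inside Grade 2 (2 × ULN, in a band from 1.5 to 3 × ULN). Grade 1 is not reached for any row.

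**2. What eligibility allows at entry (Protocol 5.1 against SAP Table 1)**

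| Row | Entry limit | Worst grade the limit allows at screening |
|---|---|---|
| Creatinine clearance | at least 30 mL/min | Grade 2 (30 to <60 mL/min) |
| ALT | up to 10 × ULN | Grade 3 (>5 to 20 × ULN) |
| Albumin | at least LLN | none |
| Platelets | at least 150,000/mm³ | at most Grade 1, and only if the laboratory's LLN is above 150 × 10⁹/L (LLN not given) |
| Alkaline phosphatase, GGT, hemoglobin, white cells, neutrophils, INR, glucose (both directions), creatinine | no limit of their own in the laboratory criterion | not limited |

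For AST the same 10 × ULN limit applies, and the APRI criterion restricts it further.

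Of the 12 rows, albumin and platelets are largely protected by screening, which leaves 12 − 2 = 10. The protection is not complete. The laboratory baseline is the last pre-dose value (SAP 7.3), and Appendix D schedules a new "Hematology/chemistry/urinalysis/coagulation panel" on Day 1, after screening.

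**3. Walk-through of the rule**

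| Subject | Baseline | Weeks 4 and 8 | Planned table | Shift table |
|---|---|---|---|---|
| A: creatinine clearance, stable | 45 (Grade 2) | 45, 45 | Grade 2 | 2 to 2, not worsened |
| B: creatinine clearance, falls | above 60 (below Grade 2) | 45, 45 | Grade 2 | worsened to 2 |
| C: ALT, falls | 8 × ULN (Grade 3) | normal, normal | Grade 3 if baseline enters the maximum, otherwise ungraded | 3 to ungraded, not worsened |

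A and B fall in the same cell of the planned table. A is counted under any window, so stating a window alone does not solve the problem. C shows why the window must also be stated.

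**4. Size**

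The documents give no baseline distribution, so the number affected cannot be computed. For scale only: if an assumed 2% to 20% of 230 subjects entered with a graded value that persisted, 230 × 0.02 = 4.6 to 230 × 0.20 = 46 subjects would be counted with no new toxicity. These percentages are assumptions, not estimates.

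**The case against.** **Other outputs carry baseline information.** SAP 5.2 summarizes baseline creatinine clearance, GGT, platelets and albumin (four of the 12 rows), with minimum and maximum. SAP 7.3 gives baseline means and mean changes for every protocol-specified laboratory parameter. Abnormalities judged to be adverse events reach the adverse event tables. This stands as mitigation. But group summaries do not show which subjects worsened. Under Protocol 6.1 a laboratory abnormality is an adverse event only if it leads to discontinuation, requires treatment, meets a protocol criterion or is judged one by the investigator.

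**A shift summary may be intended.** SAP 3.0 describes the plan as an overview, and SAP 8.0 mentions shifts. A reader might infer that the sponsor will produce no shift table. The documents do not support that; they show only that none is specified.

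**The data-scope sentence is not about timing.** SAP 7.3 says: "Data collected from the central and local laboratories, including additional laboratory testing due to an SAE, will be used in all analyses". A reader might take this to put pre-dose values into the maximum. It concerns the source of the values. Whether baseline enters the maximum is simply not stated.

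**Twelve rows are not twelve equal exposures.** Platelets and albumin are largely limited at entry, glucose supplies two rows, and creatinine overlaps with creatinine clearance. This stands: 12 of 15 measures what is unspecified, not how many subjects are affected.

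**A Treatment Period window has a cost.** SAP 4.3.4 has safety evaluated over the whole study, and treatment-emergent adverse events run to 30 days after the last dose (SAP 7.2). A grade table that stops at the end of treatment would lose later Grade 3 or 4 values, and mean changes would not show them. This stands and shapes the fix.

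**Conclusion.** The point holds as a gap in the descriptive safety analysis. SAP 7.3 leaves the window of the maximum grade unstated and uses no baseline reference in that table. For 12 of 15 rows no subject count elsewhere supplies one, and for two of those rows screening largely limits the problem. Persisting entry abnormality is therefore counted with new toxicity, which tends to overstate toxicity.

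A reader might go further and infer that the safety conclusion, or the assessment of liver toxicity, is unreliable. The documents do not support this. The hepatic criteria already compare ALT, AST and total bilirubin with baseline at higher levels, and no hypothesis test or success rule uses the grade table. SVR12 and type I error are unaffected.

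The conclusion rests on the text of the SAP and the eligibility limits. It needs no assumption about how many subjects enter with graded values, and that number remains unknown. A correction is worthwhile because it is cheap and the single-arm design offers no other reference.

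**What to change.** In SAP 7.3, before database lock:

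1. Add, for every Table 1 row, a shift table of baseline grade by maximum post-baseline grade, and report the number and percentage of subjects whose grade worsened. This also gives the SAP 8.0 rule on shifts an output to govern.
2. State that the maximum grade uses post-baseline values only. If the main table is limited to the Treatment Period, count or list post-treatment values of Grade 3 or higher separately.
3. Keep the hepatic criteria, which catch large ALT and AST rises that stay within one grade.

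Borrowing the vital-sign rule of SAP 7.4 would not be enough. Suppose a stable subject's baseline and two later values vary exchangeably, without ties and all within the graded range. The chance that at least one later value is worse than baseline is then 1 − 1/3 = 2/3, so most stable entry abnormality would still be counted.

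The cost is one statement of the window and one more descriptive table, plus a short count or listing if the window stops at the end of treatment, all from data already scheduled for collection. One limitation remains: worsening within a grade of a non-hepatic test appears only on the diagonal of the shift table.

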No trends in liver chemistry abnormalities have been observed in Phase 2 and Phase 3 studies, including in subjects with compensated cirrhosis. ALT elevation from nadir to $> 5 \times$ ULN occurred in 3/2367 (0.1%) of subjects; none of these subjects prematurely discontinued study drug due to the elevation in ALT. Similarly, Grade 3 increases in bilirubin were rare (0.4%), predominantly indirect, and without bilirubin-related AEs. There were no cases identified consistent with drug-induced liver injury.

While there is a risk for the development of amino acid substitutions conferring resistance to GLE and/or PIB in subjects who fail the therapy, it may be possible to successfully retreat these subjects.

The risk of toxicities from DDIs are addressed and mitigated by the product information, which ensures awareness of these risks by both subjects and healthcare providers. Appropriate recommendations for dose adjustments of certain medications or avoidance of coadministration with other specific medications are provided in the product information.

Pharmacological class risks include Hepatitis B Virus (HBV) reactivation with DAA treatment. As the risk of HBV reactivation in subjects treated with GLE/PIB has not been studied, HBV co-infected subjects will be excluded from the study.

Aminotransferase/platelet ratio index score ≤ 1 has a high negative predictive value in the general chronic hepatitis C population. Additional eligibility criteria of normal platelets and normal albumin as well as the absence of previous diagnosis of cirrhosis have been added to mitigate the risk of including cirrhotic subjects. Also according to WHO analysis, the potential increase in treatment availability resulting from increased access to low-cost, non-invasive monitoring and reduced risk of adverse events from liver biopsy was felt to outweigh the potential harms of false-negative case identification by APRI.⁵

Given the potential for achieving high rates of SVR in naïve non-cirrhotic subjects with HCV GT1 – GT6 infection and the favorable safety profile of GLE/PIB, the overall benefit-risk balance of the GLE/PIB regimen is, therefore, positive and supports the use in subjects with chronic HCV with compensated liver disease, including subjects with renal impairment and HIV-1 co-infection.

For further details, please see findings from completed studies, including safety data in the GLE/PIB Investigator Brochure and addendum.^{8,9}

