3.5 Safety Endpoints

Safety evaluations include AE monitoring, physical examinations, vital sign measurements, electrocardiogram (ECG), and clinical laboratory testing (hematology, chemistry including hepatic function parameters) as a measure of safety and tolerability for the entire study duration.

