7.2 Analysis of Adverse Events

Adverse events will be coded using the Medical Dictionary for Regulatory Activities (MedDRA). The actual version of the MedDRA coding dictionary will be noted in the clinical study report.

Treatment-emergent adverse events are defined as any adverse event (AE) with an onset date that is after the first dose of study drug and no more than 30 days after the last dose of study drug. Events where the onset date is the same as the study drug start date are assumed to be treatment-emergent. If an incomplete onset date was collected for an adverse event, the event will be assumed to be treatment-emergent, unless there is other evidence that confirms that the event was not treatment-emergent (e.g., the event end date was prior to the study drug start date).

The number and percentage of subjects with treatment-emergent adverse events will be tabulated by primary MedDRA System Organ Class (SOC) and preferred term (PT). The system organ classes will be presented in alphabetical order, and the preferred terms will be presented in alphabetical order within each system organ class.

Adverse Event Overview

An overview of AEs will be presented consisting of the number and percentage of subjects experiencing at least one event for each of the following AE categories:

- Any treatment-emergent adverse event;

- Treatment-emergent adverse events with a "reasonable possibility" of being related to DAAs (glecaprevir/pibrentasvir);
- Treatment-emergent adverse events of grade 3 or higher;
- Serious treatment-emergent adverse events;
- Serious treatment-emergent adverse events with a "reasonable possibility" of being related to DAAs (glecaprevir/pibrentasvir);
- Treatment-emergent adverse events leading to discontinuation of study drug;
- DAA-related treatment-emergent adverse events leading to discontinuation of study drug;
- Treatment-emergent adverse events of Grade 3 or higher with a "reasonable possibility" of being related to DAA (glecaprevir/pibrentasvir);
- Serious treatment-emergent adverse events leading to discontinuation of study drug;
- Treatment-emergent adverse events leading to interruption of study drug;
- Treatment-emergent adverse events leading to death;
- Deaths.

Adverse Events by SOC and PT

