Note: The result closest to the scheduled time point will be used, except for SVR₄ and SVR₁₂. Data must also have Study Drug End Day > 2 for all windows. Study Drug End Day 0 is defined as the day of the last dose of study drug.

Table 5. Laboratory Data, Vital Sign and PRO Instruments Visit Windows (Post-Treatment Period)

Scheduled Time	Nominal Day (Study Drug End Day)	Time Window (Study Drug End Days Range)
Post-Treatment Week 4	28	3 to 56
Post-Treatment Week 12	84	57 to 126
Final Post-Treatment Visit ^a	> 2 days after the last dose of study drug	

a. The last value within the Post-Treatment Period window will be used to define the final post-treatment value. The lower bound of this Final window is Study Drug End Day 3.

Note: The result closest to the scheduled time point will be used. Data must also have Study Drug End Day > 2. Vital signs and hematology, chemistry, urinalysis, and coagulation panels are collected at both post-treatment visits. PRO instruments are collected at PTW12/PTDC only.

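### Both hepatotoxicity lists in SAP 7.3 stop at end of treatment and the maximum-grade summary states no period, so liver elevations first seen at post-treatment Week 4 or 12 have no assured subject-level count

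*SAP*

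**What the plan says.** SAP 7.3, under Assessment of Hepatotoxicity, plans two subject counts.

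- The first takes "maximum on treatment lab values meeting the following criteria for potential hepatotoxicity". Its four rows combine ALT with total bilirubin, all as multiples of ULN, with no reference to baseline.
- The second takes "post-baseline values during the Treatment Period meeting the following criteria for hepatic laboratory parameters". Its ALT row is "ALT > 5 × ULN and ≥ 2 × baseline". AST has a matching row, and the bilirubin row needs at least 2 × ULN and a value above baseline.

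SAP 8.0, Table 3, requires Study Drug End Day 2 or earlier for every treatment-period window.

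SAP 7.3 also plans a count of subjects by maximum toxicity grade, with no period given, and change-from-baseline summaries at each visit, post-treatment visits included.

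Protocol 3.5, repeated in SAP 4.3.4, sets laboratory testing "as a measure of safety and tolerability for the entire study duration". The note to SAP Table 5 says: "Vital signs and hematology, chemistry, urinalysis, and coagulation panels are collected at both post-treatment visits". SAP 7.2 treats an adverse event as treatment-emergent if it starts after the first dose and "no more than 30 days after the last dose of study drug".

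**The concern.** The primary objective includes safety, and Protocol 2.2 names hepatotoxicity as a potential risk and HBV reactivation as a class risk not studied with this regimen. Protocol 2.2 says HBV co-infected subjects are excluded, but criterion 3 in Protocol 5.1 admits subjects with isolated anti-HBc positivity if HBV DNA is below LLOQ. Appendix D schedules the hepatitis B panel at Screening only, and Protocol 6.2 calls for further HBV tests after a confirmed ALT rise. Once treatment ends, scheduled liver chemistry is the planned signal, and neither hepatic list uses it.

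The tables headed hepatotoxicity could therefore show no subject meeting a criterion while a qualifying post-treatment ALT or ALT/bilirubin elevation sits in the database. Whether a reader finds it would depend on tables that apply other rules.

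**Working it through.** The plan states no figure for this point, so the check is to place each scheduled panel against each output.

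**Inputs.** Post-baseline chemistry: Weeks 4 and 8, and post-treatment Weeks 4 and 12 (Protocol Appendix D). Post-treatment nominal days and windows: End Day 28 (3 to 56) and End Day 84 (57 to 126) (SAP Table 5). End of treatment windows: End Day 2 (SAP Table 3). Adverse event window: 30 days (SAP 7.2).

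| Output | Post-treatment Week 4 | Post-treatment Week 12 |
|---|---|---|
| ALT/bilirubin list | Out (28 > 2) | Out (84 > 2) |
| ULN-and-baseline list | Out (28 > 2) | Out (84 > 2) |
| Maximum grade | Period not stated | Period not stated |
| Change from baseline | In, not a subject count | In, not a subject count |
| Treatment-emergent AE | In at nominal day (28 ≤ 30), if reported as an AE | Out (84 > 30) |
| SAE listing | In, if serious | In, if serious |

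**Share of panels outside both lists:** 2 of 4 = 50%.

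**Week 4 against the adverse event window.** The visit window has 56 − 3 + 1 = 54 days. End Days 3 to 30 (28 days) lie inside the 30-day limit and End Days 31 to 56 (26 days) lie outside it.

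**Why pairing matters (illustration).** Take ALT 4 × ULN with total bilirubin 2.5 × ULN at post-treatment Week 4. On treatment, this would meet the first row of the first list (ALT ≥ 3 and bilirubin ≥ 2 × ULN). In SAP Table 1 it is Grade 2 for ALT (> 3 to 5) and, separately, Grade 2 for bilirubin (> 1.5 to 3). It does not reach the Protocol 6.2 ALT trigger (> 5 × ULN), so reporting it as an adverse event would rest on the other conditions in Protocol 6.1, such as the investigator's judgement. No planned output would count the combination.

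**Baseline multiple.** Protocol 6.2 uses more than 2 × baseline; SAP 7.3 uses at least 2 × baseline. A subject going from 3 to 6 × ULN has 6/3 = 2 exactly, and meets the SAP row but not the protocol rule.

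**Scale.** Protocol 2.2 reports 3/2367 = 0.13% (printed as 0.1%) for ALT rises from nadir to above 5 × ULN. Applied to 230 subjects: 230 × 3/2367 = 0.29 expected, and 1 − (1 − 3/2367)^230 = 25% chance of at least one. This is an order of magnitude only, because no observation period is given.

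**The case against.** The best defence is that several other outputs could show a post-treatment flare, and much of it stands. It rules out four stronger readings.

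- *A reader might infer that such a flare enters no count at all.* This is not shown. SAP 7.3 limits the period where it means to, and sets no limit for the maximum-grade summary, so a post-treatment Grade 3 or 4 ALT may be counted there. A Week 4 rise that meets the Protocol 6.2 trigger can become a treatment-emergent adverse event, because Protocol 6.1 treats laboratory changes meeting those criteria as adverse events. Serious events are listed to study end.
- *That the lists work only relative to baseline.* This is true of the second list alone. The first counts on-treatment ALT above 5 × ULN (with bilirubin below 2 × ULN) whatever the baseline.
- *That the change-from-baseline tables hide a flare.* One subject rising from 0.5 to 15 × ULN moves the mean of 230 by only 14.5/230 = 0.063 × ULN, but the same table reports a maximum, where that rise would stand out. It is still neither a count nor paired with bilirubin.
- *That a nadir-based row is needed to match 3/2367.* Protocol 2.2 describes "ALT elevation from nadir to" above 5 × ULN without saying whether post-treatment values were included. Its next remark concerns stopping study drug, which fits on-treatment events at least as well. The SAP's baseline condition closely follows Protocol 6.2.

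Nor does the 30-day adverse event window contradict the on-treatment laboratory window; the two may differ by design, and SAP 7.4 also restricts its vital-sign counts to treatment. What the defence does not supply is an output that applies the hepatic criteria to the post-treatment panels.

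**Conclusion.** The point holds as a gap in assured counting. Half of the scheduled post-baseline chemistry panels lie outside both hepatotoxicity lists, and the one other subject-level laboratory count leaves its period open. This sits poorly with a safety endpoint that covers the entire study. The clearest residual gaps are a non-serious elevation after the 30-day window, and any post-treatment ALT/bilirubin combination at whatever day.

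The number of affected subjects cannot be estimated from the documents. The programme figure suggests well under one ALT event in 230 overall, and the post-treatment share is unknown. With counts this small, one subject decides whether the table reads none or some.

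The conclusion assumes that on-treatment in the first list has the same limit as the Treatment Period windows in Table 3. It is a worthwhile, inexpensive improvement and not a flaw that undermines the safety assessment.

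**What to change.** In SAP 7.3:

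1. Keep the two on-treatment lists as they are.
2. Repeat both, with the same criteria, for post-treatment values: to 30 days after the last dose, and through post-treatment Week 12. A Week 4 sample drawn after End Day 30 belongs only in the second of these.
3. For each subject meeting any criterion in any period, list all ALT, AST and bilirubin values with study day.
4. State the period of the maximum-grade summary.
5. Reconcile the baseline multiple between Protocol 6.2 (strictly more than 2) and SAP 7.3 (2 or more), or say why they differ.

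The cost is SAP wording, extra table columns and one listing; every value is already scheduled. The drawback is that rises due to relapse or another illness will also be counted, so the listing needs a comment field for the likely cause.
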